It is an international, multicenter, observational, prospective and consecutive registry of patients with cardiogenic shock in the context of acute coronary syndromes, which will have a duration of 12 months starting on October 1, 2021. Coronary units from different Latin American countries will be invited to participate in the registry through the different cardiology societies. Each country and each participating center will be assigned a number and patients will be included in the registry in sequential order by center (1-2-3-etc) to maintain the confidentiality of the data. Since patient data will be extracted from medical records, records will be anonymous and there will be no follow-up, informed

consent will not be required. The names of the participating centers in the different countries will appear in a list at the end of the publications, under the collective name of "LATIN Shock group".

Definition of cardiogenic shock (classic): Presence of systolic blood pressure ≤90 mm Hg for 30 minutes or requirement of vasopressors, inotropics and / or ventricular supports to maintain a blood pressure ≥90 mmHg, associated with signs of hypoperfusion and pulmonary congestion, in the absence of hypovolemia or arrhythmias that justify the clinical picture.

A new definition of cardiogenic shock has recently been proposed, which includes 5 categories¹²:

- A- At risk: Patient who does not present signs or symptoms of cardiogenic shock but is at risk of presenting it. Includes acute myocardial infarction, previous infarction, decompensated acute or chronic heart failure.
- B- Pre-shock: It is defined when there is tachycardia or hypotension without hypoperfusion. These patients must be closely monitored and carefully treated to avoid the development of classic cardiogenic shock.
- C- Classic: Patient with hypoperfusion requiring intervention (inotropics, vasopressors, or mechanical support) despite fluid resuscitation to restore perfusion.
- D- Worse: Patient similar to category C but worsening and unresponsive to initial interventions.
- E- Extreme: Includes cases where the futility of the treatment is evaluated and palliative treatment should be considered. In turn, all these categories are discriminated according to whether or not they have suffered cardiac arrest.

In this work, patients with cardiogenic shock C, D and E will be considered as a group. It will be recorded if they have presented cardiac arrest.

Inclusion criteria:

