Patients of both sexes and older than 18 years, admitted to a coronary or polyvalent critical care unit, for an acute coronary syndrome with or without ST-segment elevation who present with cardiogenic shock from admission or develop it during hospitalization and who can be followed up in its evolution until hospital discharge

Exclusion criteria:

Non-ischemic cardiogenic shock (chronic heart failure, myocarditis, sepsis, tachycardiomyopathy, Takotsubo, etc.). Cardiogenic shock A and B of the new SCAI classification.

Information gathering:

The following variables will be analyzed: age, sex, risk factors and comorbidities, previous treatment, characteristics of the AMI that generated the shock, location of the infarction, Killip and Kimball on admission and evolution, time of evolution on admission, reperfusion strategies (fibrinolysis or angioplasty), if angioplasty was required: what type (primary, rescue, delayed), number of vessels operated, drug treatment instituted, hemodynamic monitoring and mechanical support (balloon pump, ECMO, mechanical ventilation, others).

The in-hospital evolution and eventual complications (fever, sepsis, COVID 19, multiorgan failure, arrhythmias, reinfarction, post-infarction angina, mechanical complications, transfusion requirement, major and minor bleeding) will be studied. Laboratory data will be collected upon admission and at 24 hours. Hemodynamic measurements will be recorded at the time of Swan Ganz catheter placement and at 24 hours (if used) and echocardiogram data. The follow-up will only be in-hospital.

The data will be collected by the researchers from the different participating centers through an electronic file developed ad hoc in Red Cap and the data will be analyzed by the executive committee that will be made up of members of the research area of the Argentine Society of Cardiology.

The Red Cap platform is a secure web application for online data management. The data will be stored securely on a server at the Argentine Society of Cardiology. For centers without Internet access, it is possible to collect data offline through Red Cap using the Red Cap mobile application that is downloaded to a tablet or mobile device. With the app, data can be collected offline and then synced with Red Cap's server. While Attachment 1 can also be printed and used to collect data for subsequent electronic submission, direct collection of electronic data is preferable to avoid transcription errors.

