As it is a study that involves different countries, the data will be analyzed globally and by country initially. Different sub-studies may be carried out with the information obtained. Each participating country has the right to submit ideas for conducting sub-studies. In that case, they must be formally presented to the Executive Committee, who will carry out the analysis and provide the data if the proposal is accepted. The sub-studies should be re-evaluated by the ethics committee.

Each participating Scientific Society will receive an Excel with the data of their country once the study is finished (anonymized data) that they can present at conferences or for publication as national experiences. Each participating center

will have available immediately statistical reports (automatically generated) of the patients who have entered their center.

File in Red Cap: http://redcap.sac.org.ar/redcap/surveys/?s=RMCAYAXMF3

Statistic analysis:

The information obtained will be incorporated into a database that will be analyzed using the statistical programs Epi-info and / or IBM SPSS. For each of the observed variables, a frequency table will be constructed.

Continuous variables will be expressed as mean and standard deviation for those with a normal or Gaussian distribution and as a median with an interquartile range 25% -75% for those without such distribution. The comparison between these variables will be carried out using the Student's t test or the Wilcoxon ranksum test, as appropriate.

Discrete variables will be expressed as percentages. Statistical comparisons between them will be made using the chi-square test with Yates correction or Fisher's exact test, as appropriate.

Contingency tables will be constructed to analyze the association or independence of the variables. The analysis of the existence of associations and / or independent predictions between the different variables involved and the end points will be carried out by means of linear regression analysis and / or multiple logistic. The variables of univariate statistical significance will be entered for evaluation in the different regression models. The value corresponding to each covariate of the aforementioned analysis will be expressed as adjusted Odds Ratio and its corresponding 95% confidence interval. All statistical comparisons will be two-tailed, and p values <0.05 will be considered statistically significant.

Consent of the patient

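### For Objective 4, variables enter the mortality model on univariate significance with no time zero and no limit on when they were measured, so survival-dependent variables and near-proxies of death can be admitted

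*Combined protocol and SAP*

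**What the plan says.** Objective 4 (section Objetives) is to evaluate predictors of in-hospital death. The Statistic analysis section plans linear and/or multiple logistic regression to look for "independent predictions between the different variables involved and the end points", reported as adjusted odds ratios with 95% confidence intervals. The only rule for building the model is "The variables of univariate statistical significance will be entered for evaluation in the different regression models". For categorical variables the screen is "the chi-square test with Yates correction" or Fisher's exact test, and "p values <0.05 will be considered statistically significant", two-tailed.

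Under Information gathering, a list opening "The following variables will be analyzed" includes "Killip and Kimball on admission and evolution", the type of angioplasty (primary, rescue or delayed) and mechanical support. The same section collects complications of the stay, including sepsis and multiorgan failure. Laboratory values are taken on admission and at 24 hours, and Swan-Ganz values at catheter placement and at 24 hours.

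The Inclusion criteria admit patients in shock on admission and patients who develop it later in the stay. No section names a time zero for the mortality model, limits candidates by when they were measured, plans a landmark or time-dependent analysis, or says how missing values or deaths before 24 hours are handled.

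**The concern.** A predictor needs a moment at which the prediction is made. Without one, the entry rule treats a fact known at the door and an event on a later day as equal candidates. Three kinds of variable can then enter.

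- Variables that can be recorded only if the patient lives long enough, such as delayed angioplasty or a late complication. Early deaths are counted as not having them, so they tend to look protective even with no effect on death.
- Near-proxies of death, such as multiorgan failure, which may be part of the process of dying. These are biased the other way.
- 24-hour values, which the earliest deaths do not have. In a complete-case model those patients drop out, and the result describes only patients who lived to be sampled.

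Ordinary adjustment does not cure the first two, because the fault lies in how the variable is defined in time. At stake is the list of predictors reported for Objective 4: a variable may reach the model because of when it could be recorded, and not because it carries prognostic information.

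**Working it through.** **Inputs from the documents.** About 500 patients (Sample, under Participating Centers). Mortality of 40-50% (Introduction, a background figure). Yates chi-square at two-sided 0.05 (Statistic analysis). The 500 is an enrolment estimate with no power or precision calculation behind it, so there is nothing to reproduce. Deaths: 500 × 0.40 = 200 to 500 × 0.50 = 250. At 45% there are 225 deaths and 275 survivors.

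**Inputs assumed (not in the documents).** f, the share of deaths before 24 hours; p, the prevalence of the variable; g, the share of deaths otherwise without the variable in which it is recorded as part of dying.

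**1. No-effect variable recordable only after 24 hours.** Prevalence is p in survivors and (1−f)p in deaths, so OR = (1−f)(1−p) / (1−(1−f)p). With f = 0.25 and p = 0.30: (0.75 × 0.70) / (1 − 0.225) = 0.525/0.775 = 0.68. The chance of passing the screen comes from exact enumeration of two-by-two tables with 225 deaths and 275 survivors. Each cell gives OR, then chance of entry:

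| f | p = 10% | p = 30% | p = 50% |
|---|---|---|---|
| 0% | 1.00, 3% | 1.00, 4% | 1.00, 4% |
| 5% | 0.94, 4% | 0.93, 5% | 0.90, 7% |
| 15% | 0.84, 6% | 0.80, 17% | 0.74, 35% |
| 25% | 0.73, 12% | 0.68, 43% | 0.60, 78% |
| 35% | 0.63, 23% | 0.57, 74% | 0.48, 97% |

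With 200 or 250 deaths the entry chances move by at most about 2 percentage points. The table does not describe support started in the first hours.

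**2. No-effect variable also recorded as part of dying.** OR = (p + (1−p)g) / (p(1−g)). With p = 0.20 and g = 0.10: 0.28/0.18 = 1.56, entry chance 51%. At p = 0.20, g = 0.05 gives 1.26 and 16%, and g = 0.20 gives 2.25 and 97%.

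**3. The two can cancel.** With f = 0.25, g = 0.10 and p = 0.20, prevalence in deaths is 0.75 × 0.28 = 0.21, and OR = (0.21/0.79) / (0.20/0.80) = 1.06.

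**4. 24-hour values with complete cases.** Deaths lost = 225f; at f = 0.25, about 56. Analysed mortality = (225 − 56.25) / (500 − 56.25) = 168.75/443.75 = 38%, against 45%. At f = 5% and 35% the losses are about 11 and 79 deaths, and analysed mortality is 44% and 35%.

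**5. Sensitivity to the timing model.** Step 1 gives late deaths and survivors the same chance of the variable. A simulation instead let a no-effect exposure accumulate over the stay (assumed 0.05-0.3 per day; 20-50% of deaths within 24 hours, the rest over days 1-10; discharge on days 5-15; mortality 40% and 50%). It gave median odds ratios of 0.06-0.38, with p<0.05 in 99.3-100% of runs. A 24-hour landmark on the same data gave 0.97-1.06 and 1.8-4.8%, with 374-460 of the 500 patients analysed. The direction is stable; the size depends on the assumptions.

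**The case against.** The strongest case against is that the plan permits these variables but does not commit to them. Candidates are entered for evaluation, retention is left open, sensible investigators would set aside obvious proxies, and the Ethical considerations section calls the study descriptive. That limits the claim but does not remove it. The written rule contains nothing that would exclude such variables, and the section still promises independent associations with adjusted odds ratios. No causal reading is needed for the timing problem to arise.

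Four stronger readings are tempting, and the documents do not support them.

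- A reader might infer that survival-dependent variables will end up as reported independent predictors. Only univariate entry was calculated; no adjusted estimate can be derived from the documents.
- A reader might take any of the odds ratios above as the expected bias. Every timing input is assumed, the two timing models give different ranges, and opposite biases can cancel.
- A reader might cite cardiac arrest as a near-proxy of death, because "It will be recorded if they have presented cardiac arrest" carries no timing. That sentence closes the description of the SCAI categories, which are split by whether arrest has occurred. It reads more naturally as that qualifier than as the mode of dying, so multiorgan failure is the sounder example.
- A reader might infer that early deaths will be dropped. That happens only if a 24-hour value is put in the model and complete cases are used; the plan states neither.

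It is also fair to say that Attachment 1, the data form, is not in the text and may record event times. Even so, the analysis section makes no use of them.

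**Conclusion.** The point holds as a gap in a stated rule: for Objective 4, univariate significance admits candidates whatever their timing, so survival-dependent variables, near-proxies of death and 24-hour values can all reach the mortality model. The direction of each bias is clear. The size is not computable from the documents and ranges from none to large; OR 0.68 with 43% entry (against 4% with no early deaths) is one illustration. It rests on 500 patients, 45% mortality, an assumed 25% of deaths before 24 hours and an assumed 30% prevalence. The complaint is about timing. It is not a general case against univariate screening, and the fix leaves that screen in place. Objectives 1, 2, 3 and 5 are not affected. Cheap improvement.

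**What to change.** Add one paragraph to Statistic analysis that does the following for Objective 4.

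- Name in-hospital death as the end point and one time zero, for example onset of shock, or admission.
- List the eligible candidates: variables known by time zero and obtainable in every patient, whether shock is present on admission or comes later. Examples are age, sex, risk factors, comorbidities, previous treatment, infarct characteristics and location, and Killip class and laboratory values on admission. If time zero is shock onset, add shock on admission versus later.
- Do not enter in-hospital measurements that can exist only in later-onset patients. They are absent by construction for patients in shock on admission, and a complete-case model would drop all of those patients.
- Report later treatments, complications and 24-hour values descriptively under Objectives 2 and 3.
- If 24-hour values are used prognostically, fit a separate landmark model in patients alive and in hospital at 24 hours. State from which moment the 24 hours run, label the model as conditional on 24-hour survival, and report the number of earlier deaths.

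The cost is that paragraph and, if time zero is shock onset, a check that the data form separates shock on admission from later shock. The main model can still draw on all of the roughly 500 patients. The downside is that treatments and complications after time zero are no longer reported as independent predictors. A rule for missing values among the eligible candidates would still have to be stated separately.

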Latin American Registry of Cardiogenic Shock in the context of Acute Coronary Syndromes (LATIN-Shock)

Investigation area Argentine Society of Cardiology

Index

Introduction	3
Objetives	3
Methods	3
Study design	
Inclusion criteria	
Exclusion criteria	
Information gathering	
Statistic analysis	
Ethical considerations	
Study organization	
Publications	
Bibliography	

Introduction:

Cardiogenic shock is a rare disease, but it constitutes the main cause of mortality in patients hospitalized for acute myocardial infarction. Its incidence ranges between 7 and 10% of infarction cases ¹ and it is associated with a mortality of 40-50% despite revascularization and the use of intra-Aortic Balloon Contrapulsation ²⁻³⁻⁴.

Most of the bibliography on this topic is North American, it is already many years old ⁵⁻⁶ and the one that is currently published mainly shows the results of different ventricular supports that are not commonly used in our environment ⁷. So far there is no record that reports the reality of Latin America. Only in Argentina, has carried out a national registry of cardiogenic shock in the context of acute coronary syndromes but have already spent more than 5 years since its publication⁸. In recent years have even changed management guidelines this pathology ⁹⁻¹⁰ and works have been published that could have changed previous behaviors ¹¹.

This is a project of the Argentine Society of Cardiology to collect epidemiological data and current management of cardiogenic shock in Latin America.

Objetives:

- 1- Determine the clinical characteristics of patients who are admitted to the coronary unit with acute coronary symptoms and present Cardiogenic Shock, either from admission or during their in-hospital evolution.
- 2- Analyze the treatment of patients with cardiogenic shock.
- 3- Observe the clinical in-hospital evolution.
- 4- Evaluates predictors of in-hospital mortality.
- 5- Compare the clinic, management and evolution characteristics in the different participating Latin American countries.

Methods:

Study design:

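### Univariate significance is the only stated entry rule for the regression models, so a masked covariate can be missing from the adjusted odds ratios for in-hospital mortality

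*Combined protocol and SAP*

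**What the plan says.** Objective 4 in the Objetives section is: "Evaluates predictors of in-hospital mortality". The Statistic analysis section serves it with linear and/or multiple logistic regression, aimed at "associations and / or independent predictions between the different variables involved and the end points". On which variables go into the models it has one sentence: "The variables of univariate statistical significance will be entered for evaluation in the different regression models". No separate screening threshold is given; the only one available is the general rule, "All statistical comparisons will be two-tailed, and p values <0.05 will be considered statistically significant". On reporting it says: "The value corresponding to each covariate of the aforementioned analysis will be expressed as adjusted Odds Ratio and its corresponding 95% confidence interval".

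The documents name no covariate that stays in whatever its p-value. They describe no looser screen, shrinkage, validation or interval that allows for selection. They also do not forbid further covariates.

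**The concern.** A univariate test asks whether a variable is related to death on its own. Whether it matters after adjustment is a different question, and the plan's wording about independent prediction and adjusted odds ratios promises an answer to that second one. The two can differ when candidates are correlated. Suppose two variables are positively correlated, one raises the risk of death and the other lowers it. Each then hides part of the other's effect, and the weaker may look inert alone. The screen drops it, and the stronger variable is reported as adjusted when it is not adjusted for the variable that mattered.

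Two things are at stake: the odds ratio and interval of the variable that stays, and the reading of the variable that was dropped, whose absence can be taken to mean that it is not a predictor. The Information gathering section lists related candidates (comorbidities, infarct features, Killip class, reperfusion, drugs, mechanical support), so masking is plausible, but the documents do not show that it occurs.

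**Working it through.** The plan has no figure of its own on this point to reproduce. Its sample of about 500 is a recruitment estimate with no power or precision calculation behind it.

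**Inputs from the documents.** About 500 patients (Study organization, Sample). Mortality from the Introduction: "it is associated with a mortality of 40-50% despite revascularization". Deaths: 500 × 0.40 = 200 to 500 × 0.50 = 250. Screen: two-sided p<0.05.

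**Assumed inputs.** Two standard-normal variables with correlation r, and true odds ratios per SD of OR1 and OR2. The documents give none of these.

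**Hand check.** Ignoring the small non-collapsibility of the odds ratio:

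- second variable alone: log-OR ≈ ln(OR2) + r × ln(OR1)
- first variable with the second left out: log-OR ≈ ln(OR1) + r × ln(OR2)

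Main case, OR1 = 1.60, OR2 = 0.79, r = 0.5:

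- second alone: −0.236 + 0.5 × 0.470 = −0.001, odds ratio about 1.00. The inputs were chosen to cancel almost exactly, so the second variable should pass at about the 5% false-positive rate.
- first with the second left out: 0.470 − 0.5 × 0.236 = 0.352, odds ratio 1.42 instead of 1.60.
- standard error at 45% mortality ≈ 1/√(500 × 0.45 × 0.55) = 0.090. The shift of 0.118 is therefore about 1.3 standard errors, enough to take a nominal 95% interval well below 95%.

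**Simulation.** n = 500, 2,000 to 4,000 datasets per setting. Rule: univariate logistic test, then one logistic model with the variables that passed. Comparator: both variables always kept. Coverage under the rule is counted where the first variable itself entered (96-97% of datasets in the main case). In the main case the first variable's median odds ratio was 1.43 under the rule and 1.61 with both kept; coverage with both kept was about 95%.

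| OR2 (OR1 = 1.60) | r | Second alone, approx. OR | Second enters | Coverage for first, under the rule |
|---|---|---|---|---|
| 0.79 | 0.5 | 1.00 | about 5% | about 77-80% |
| 0.90 | 0.5 | 1.14 | 29% | about 91% |
| 0.70 | 0.5 | 0.89 | 27% | about 68% |
| 0.60 | 0.5 | 0.76 | 83% | about 84-86% |
| 0.79 | 0.3 | 0.91 | – | about 90-91% |
| 0.79 | 0.2 | 0.87 | – | about 94% |
| 0.79 | 0 | 0.79 | – | about 95% |
| 1.27 (same direction) | 0.5 | 1.61 | – | about 95% |

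**A second design.** Binary exposure and confounder, 3,000 datasets per setting. Confounder prevalence 30%; exposure prevalence 70% with it and 30% without; exposure and confounder odds ratios 0.5 and 2.0, 0.4 and 1.8, or 0.5 and 1.5. The confounder failed the screen in 47%, 81% and 90-91% of datasets. Where it was left out, coverage for the exposure was 83-84%, 82-83% and 89-90%, against about 95% when it was always kept. Counting only datasets in which the exposure also passed the screen, coverage was about 98%, 86-87% and 99%, so on that count only the middle setting shows undercoverage.

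**The case against.** Several objections have force.

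- **The main case is tuned.** It is: entry at about 5% follows from exact cancellation and says nothing about this registry. But the harm does not vanish away from that point. With OR2 = 0.70 the second variable enters more often, yet coverage is lower, at about 68%.
- **Harm needs opposite effects and sizeable correlation.** This stands. A reader might infer that the registry's odds ratios will be wrong by the amounts above; the documents give no correlations or effect sizes, so that does not follow.
- **The comparator always contains the confounder.** This stands too. The gains are best cases: a clinical list that misses a confounder is biased in the same way.
- **The text does not ban other covariates.** A reader might infer that it does. It says only that screened variables are entered for evaluation, which leaves later modelling open. But no other route into the model is stated, so an analyst who follows the text meets the problem.
- **The objective is prediction and no exposure is named.** This weakens the language of confounding. The plan's own promise of independent prediction and adjusted odds ratios keeps the point alive.

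A reader might also infer that the screen produces extra false predictors compared with a fixed list. The calculations do not support that. With 30 assumed candidates, 8 of them true predictors with mixed-sign effects, and r = 0.2, at least one false predictor appeared in 31-34% of datasets under the rule and in 34% with a fixed list of 15.

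**Conclusion.** The point holds as a weakness of method with a cheap remedy. The only stated entry rule can leave out a masked covariate, and the plan then reports ordinary adjusted odds ratios and intervals as if nothing had been selected. Under the assumed two-variable settings with r = 0.5 and opposite effects, coverage runs from about 68% to 91%. At r = 0.3 it is about 90-91%, and at r of 0.2 or less, or with same-direction effects, little or nothing is lost. These figures rest on assumed correlations and odds ratios, on the general 0.05 rule being the screening threshold, and on a comparator that includes the right variable.

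It is not a threat to the registry as a whole. Mortality predictors are one of five unranked objectives, and the Ethical considerations section calls the study descriptive. The change should be made, but the other objectives do not depend on it.

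**What to change.** Replace the entry sentence in the Statistic analysis section with:

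> For the pooled model of in-hospital mortality, a short list of covariates chosen on clinical grounds will be fixed by the executive committee before outcome data are examined; all will be kept whatever their p-value and all reported with their estimate and 95% CI. Any wider or data-driven search, including selection by univariate significance, will be labelled exploratory.

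The committee is the natural owner, since the Information gathering section already says that "the data will be analyzed by the executive committee".

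Size the list by model parameters, because a variable with k categories uses k − 1. Items such as "location of the infarction, Killip and Kimball on admission and evolution" therefore count more than once. With 10-15 parameters, 200/15 = 13.3 and 250/10 = 25, or about 13-25 deaths per parameter. This holds only for the pooled model of about 500 patients. The plan also analyses the data by country, and those models need a shorter list or should stay descriptive.

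Cost: one sentence and some committee time before outcomes are examined, with no new data and no new regression method. The downside is fewer headline predictors and a result that relies on the clinical choice of list.

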LATIN-Shock, as an observational study, only requires data that has already been collected and is available in the patient's medical record. It does not require sensitive data. It does not involve specific interventions and there is no follow-up after discharge, therefore, informed consent is not required. However, this could be adjusted according to local regulations of the participating countries.

Ethical considerations

The protocol and the registration form will be submitted for approval by the ethics committee of the Sociedad Argentina de Cardiología, [name]. The study will be carried out in accordance with national and international ethical standards (CABA Law No. 3301, Declaration of Helsinki, and others).

As it is a descriptive study in which the data will be those normally collected in this pathology and there will be no identification of the patient or out-of-hospital follow-up, the signing of informed consent will not be required.

Study organization:

Executive committee:

Directors: [name] - [name]

Scientific and organizational secretariat: It is responsible for the organization of research, control, management and preparation of data analysis reports. It will be made up of: [name], [name], [name].

Each participating Latin American Society of Cardiology will be represented by one / two members (designated by its president) and they will be the ones who appear in the final document and receive the database of their country at the end of the study.

Collaborators: This is the name given to the members of the centers where the inclusion of the participants takes place. The head of each center where the investigation is carried out and another doctor designated by him will be specially invited, who will be in charge of preparing the registration forms.

Participating Centers:

Other Spanish-speaking Latin American Cardiology Societies will be invited to participate and they will designate the coronary units where the registry will be carried out.

Sample: It is estimated to include approximately 500 patients in one year.

Publications

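### As planned, the by-country comparison does not separate country from the type of hospital each society designates, because no common selection rule is stated and the protocol text lists no centre characteristic

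*Combined protocol and SAP*

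**What the plan says.** Under Study design, recruitment runs through the societies: "Coronary units from different Latin American countries will be invited to participate in the registry through the different cardiology societies". Under Participating Centers, the other Spanish-speaking societies are invited and "they will designate the coronary units where the registry will be carried out". Neither place gives a criterion, a sampling frame or a quota by hospital type. How the Argentine units are chosen is not described beyond the general invitation.

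More than one kind of unit is eligible. The inclusion criteria take patients "admitted to a coronary or polyvalent critical care unit".

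The list under Information gathering opens "The following variables will be analyzed: age, sex, risk factors and comorbidities, previous treatment, characteristics of the AMI that generated the shock". It goes on to reperfusion, drugs, monitoring, mechanical support, complications, laboratory, haemodynamic and echocardiographic data. All of these are recorded per patient. The one centre-level item in the text is an identifier: "Each country and each participating center will be assigned a number".

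Objective 5 is: "Compare the clinic, management and evolution characteristics in the different participating Latin American countries". The analysis follows it: "the data will be analyzed globally and by country initially". The Statistic analysis section sets two-sided tests at the 5% level and names no stratification or adjustment by centre or centre type. The Introduction motivates the registry with the statement "So far there is no record that reports the reality of Latin America".

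**The concern.** Each society may apply its own idea of a suitable unit. One might name mainly referral hospitals with catheterisation and mechanical support, and another a broader mix. A table by country would then show the mix of hospitals together with whatever differs between the countries, and the variables listed would not let a reader tell how much is which.

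The exposure is greatest for management. Whether a patient receives angioplasty, a balloon pump or ECMO depends directly on what the hospital has. These treatments are recorded, but they cannot stand in for hospital type, because they are the outcomes that Objective 5 compares. Nor would a random effect for centre solve it: that corrects standard errors for correlation within centres but does not remove a systematic difference in the kind of centre enrolled.

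At stake is the reading of Objective 5, and of any national publication made from the country data sets.

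**Working it through.** **What the documents give.** The plan has no figure to reproduce here. The sample of about 500 is a recruitment estimate without effect size, power or split by country. The gap itself is established by reading: designation without a stated rule, no centre descriptor in the variable list, and a comparison by country with no centre-type analysis.

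**How large could the effect be?** This is an illustration, and every input except the test level is assumed.
- No true country effect: within a centre type, rates are the same in every country.
- Balloon pump use: 50% in equipped centres, 10% in others.
- Mortality: 40% in equipped centres, 50% in others. These two values are the ends of the range in the Introduction, but that range comes from the literature and is not a contrast between centre types.
- Patients per country: 125, which is 500 / 4 for four equal countries. The number of countries is not stated.
- Share *s* of a country's patients from equipped centres: 90% versus 30%, or 80% versus 50%.
- Two-sided 5% test, as in the Statistic analysis section.

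**Country rates**

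Use = 0.50*s* + 0.10(1 − *s*). Mortality = 0.40*s* + 0.50(1 − *s*).

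- *s* = 0.9: use 0.45 + 0.01 = 46%; mortality 0.36 + 0.05 = 41%.
- *s* = 0.3: use 0.15 + 0.07 = 22%; mortality 0.12 + 0.35 = 47%.
- *s* = 0.8: use 0.40 + 0.02 = 42%; mortality 0.32 + 0.10 = 42%.
- *s* = 0.5: use 0.25 + 0.05 = 30%; mortality 0.20 + 0.25 = 45%.

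**Chance of p < 0.05**

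With d = |p₁ − p₂| and p̄ the mean of the two rates, the normal approximation is Φ{[d√n − 1.96√(2p̄(1 − p̄))] / √(p₁(1 − p₁) + p₂(1 − p₂))}.

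For 46% versus 22%: d√n = 0.24 × 11.18 = 2.683; 1.96 × √(2 × 0.34 × 0.66) = 1.313; denominator √(0.2484 + 0.1716) = 0.648. So Φ(1.370 / 0.648) = Φ(2.11) = 98%.

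The last column is an exact binomial calculation with the Yates correction that the protocol names.

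| Outcome | Mix | Country rates | No correction | Yates |
|---|---|---|---|---|
| Balloon pump | 90% v 30% | 46% v 22% | 98% | 98% |
| Balloon pump | 80% v 50% | 42% v 30% | 51% | 46% |
| Mortality | 90% v 30% | 41% v 47% | 16% | 13% |
| Mortality | 80% v 50% | 42% v 45% | 7% | 6% |

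**Sensitivity.** With 50 patients per country, 42% versus 30% is significant about 18% of the time with Yates. With two countries of 250 and the same assumed mortality rates, an 80% versus 20% mix gives 42% versus 48% (27% without correction), and a 60% versus 40% mix gives 44% versus 46% (6.5%).

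**The case against.** **The form is not in the text.** The data are collected on Attachment 1 and the REDCap file, and neither could be seen. A reader might infer that no centre characteristic is collected at all. The documents do not support that; they show only that the protocol text lists none. This stands, and the fix allows for it.

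**The two are not inseparable in principle.** A reader might also conclude that country and hospital type can never be told apart. That goes too far. Patients are numbered within centre, and the centres will be named in the publications, so centre type can be attached wherever types overlap between countries. But the plan does not provide for this, and where a country contributes a single type, no stratified table can separate them.

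**Designation is not favouritism.** Nothing suggests that societies pick units to flatter their results. The text says only that they designate them, and says so only for the societies other than the Argentine one.

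**The registry is descriptive, and facilities may be part of a country's care.** This is the strongest point. If a country's hospitals seldom have mechanical support, stratifying by availability could hide what the registry wants to show. It is a reason to keep the overall country result as the descriptive one and set the stratified result beside it. It does not answer the concern, because an overall result reflects the country's facilities only if the designated units do, and no rule secures that. The sentence about Latin American reality is motivation and should not be read as a claim of representativeness.

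**The inputs are invented, and mortality is little affected.** Both are true. The illustration shows what is possible, not what will happen.

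**Conclusion.** The concern holds for the plan as written. Designation without a stated criterion, a variable list confined to patients, and a tested comparison by country leave country and hospital type mixed in Objective 5.

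Under the stated assumptions, hospital mix alone could make balloon pump use differ by 12 to 24 points between countries, significant in roughly half to nearly all repetitions. Mortality would differ by 3 to 6 points and would seldom reach significance (about 6 to 16%). The point therefore bears mainly on management that depends on facilities. It does not support a claim that spurious mortality differences are likely.

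It limits the interpretation of one of five objectives and does not invalidate the registry: describing the enrolled patients, their treatment and their course is unaffected. It is worth acting on because the remedy is cheap.

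**What to change.** 1. When each centre receives its number, complete a one-time centre form in REDCap, unless the existing form already holds these items: 24-hour angioplasty, balloon pump and ECMO on site, cardiac surgery on site, public or private, and yearly infarction volume. List the items in the protocol.
2. For Objective 5, report country results overall and also within centre type (with or without on-site angioplasty and mechanical support). Treat the overall result as the descriptive one, since available facilities may be part of a country's care.
3. Where a country contributes only one centre type, say that country and centre type cannot be separated there.
4. Word conclusions as applying to participating centres in country X, not to the country's practice.

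The cost is one short form per centre, one additional table and a wording rule. No patient-level data are added. The drawbacks are thin or empty strata in small countries and a more modest claim.
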